components: (1) performing the caregiving role, and (2) caring for one’s own health. **We hypothesize that CGs in the intervention group will show significantly greater reductions in anxiety, depression, and fatigue, and significantly greater improvements in HRQOL than subjects in the control group. We also hypothesize that the intervention will improve CG skills and ability to solve problems, resulting in greater improvements in patient HRQOL and fewer interrupted treatment courses, unplanned admissions, unplanned emergency room visits, and unplanned use of IV fluids than those experienced by patients in the control group.**

Figure 2
Revised Study Model and Related Aims

For this study, all patients (regardless of diagnosis or treatment course) have documented high symptom burden associated with significant functional impairment.^{18,23,27,31} Their CGs also face similar challenges in coping with their loved ones’ intense physical treatment side effects (e.g., skin breakdown, nutritional/hydration issues), and mental health issues. However, in order to account for differences due to population diversity and the potential influences on outcomes, we will track and use as covariates (potential moderators) several **patient illness factors** (variables) most relevant to the population and the outcomes of interest. These include cancer stage, time since diagnosis, treatment type (chemoradiotherapy versus radiotherapy alone), HPV status (in HNC and anal cancer), palliative care use, and patient performance status. **Care demands**, defined as hours/week spent caregiving, **patient and CG demographic characteristics** (race, marital status, employment status, socioeconomic status), and **use of mental health interventions** (support group participation, social work and/or psychologist involvement) will be assessed as covariates.

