2.0 OBJECTIVES

The aims of this 2-group, prospective, randomized controlled design are:

Aim 1: Evaluate the effect of a CG intervention, as compared to a control group, on CG primary (anxiety) and secondary (depression, HRQOL, and fatigue) outcomes.

Aim 2: Measure the effect of the intervention, as compared to a control group, on patient outcomes (HRQOL and interrupted treatment course), and healthcare utilization outcomes (unplanned hospital admissions, unplanned emergency room visits, and unplanned use of intravenous [IV] fluids).

Aim 3: Determine if CG self-efficacy mediates the effect of the intervention on CG anxiety.

Aim 4: Determine if patient illness factors, care demands (hours per week spent caregiving), and patient and CG demographic factors moderate the relationship between the intervention and CG outcomes.

Aim 4a: Examine which social determinants of health (aspects of vulnerability) in caregivers moderate the efficacy of the intervention.

Aim 4b: Explore caregivers' perspectives and experiences regarding the intervention to understand how the intervention should be modified to better serve vulnerable caregivers.

Aim 5: Compare the costs of healthcare utilization (unplanned hospital admission, unplanned emergency room visits, and unplanned use of IV fluids) between the intervention and control groups.

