6.0 STATISTICAL ANALYSIS

6.1 Primary and secondary endpoints.

The primary endpoint is difference in caregiver anxiety between the intervention and control groups at 20

weeks post-radiation treatment. Secondary endpoints are caregiver anxiety at the end of radiation treatment and 4 weeks post treatment; caregiver depression, HRQOL, and fatigue at the end of treatment and 4 weeks post-treatment; and patient HRQOL at the end of treatment and 4 weeks post-treatment.

6.2, 6.7, 6.8 Statistical Design, Power, Analysis plan, & Missing data.

An intent-to-treat analysis is planned. Before carrying out inferential statistical procedures, exploratory data analysis will be performed: all variable distributions will be examined and descriptive summary statistics will be provided: including means, standard deviations, and ranges for continuous variables, as well as percentages and frequencies for categorical variables, will be provided to describe the study sample. Variable transformations will be made in cases where distributions are skewed, or otherwise fail to meet the assumptions for analyses; nonparametric procedures will be used where transformations would be inappropriate. Plots will be used to describe the data and identify outliers and influential observations.

Aim 1

Analysis. The primary analysis for Aim 1 will be to compare the control and CG intervention arms with respect to CG anxiety at T4 (20 weeks postradiation treatment). A linear mixed model repeated measures analysis will be used to obtain mean changes from baseline in anxiety scores at Times T2, T3, and T4, using baseline anxiety as a covariate, also adjusting for covariates described in Table 4. A contrast of means will be constructed to compare arms with respect to change in anxiety at T4 (primary analysis) at the 0.05 significance level. In addition, the baseline characteristics of the two treatment groups will be compared using appropriate 2-sample tests for continuous or binary outcomes, and in a secondary analysis, characteristics found to differ between groups at baseline will be adjusted for in the linear mixed model. A secondary analysis will test for differences between groups at the other postbaseline time points, using the Tukey method to control the familywise error rate on a per outcome basis. Other CG outcomes will be compared between groups using a similar approach.

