Power. With 180 subjects randomized and a 10% dropout rate, the sample size for the primary analysis will be 162 CGs (81 per arm). Assuming a correlation of 0.50 between CG anxiety scores at baseline and T4, when adjusting for baseline anxiety, a difference in means of 0.36 standard deviations (*SDs*) can be detected with 80% power using a 2-sided test with significance level 0.05, where *SD* is the within-group standard deviation of anxiety scores at Time T4. Here, adjustment for baseline anxiety reduces the detectable effect size from 0.41 to 0.36. This effect size (Cohen's *d*) is intermediate between a "small" (0.2) and "moderate" effect size, as defined by Cohen,¹⁰⁶ and is close to the pooled estimate of 0.29 from a meta-analysis of interventions (psychoeducational, skills training, and therapeutic counseling) with family CGs of cancer patients.² For other outcomes, there is 80% power to detect effect sizes of 0.41 *SDs* with a 2-sided test, significance level 0.05.

Aim 2

Analysis. This aim is to measure the effect of the intervention, as compared to a control group, on patient outcomes (HRQOL, interrupted treatment course) and healthcare utilization outcomes (unplanned hospital admissions, unplanned emergency room visits, and unplanned IV fluid use). Most outcomes will be count variables enumerating the cumulative numbers at T2, T3, and T4, which can be analyzed using Poisson regression methods implemented as generalized linear models, possibly allowing for overdispersion. Zero-inflated Poisson or negative binomial models^{107,108} will be considered if the data indicate a higher frequency of zeros than predicted by a Poisson model. HRQOL, a continuous measure, will be analyzed using a linear mixed model with repeated measures at T1, T2, T3, and T4. We will analyze the effect of the intervention on HRQOL across diagnoses using the common FACT subscales and will describe the symptom experience within each diagnostic group using the cancer-specific FACT subscale.

Power. From our pilot study, in the control group we expect means of 0.29 and 0.25 for the number of unplanned missed days and number of unplanned hospital admissions, respectively. In a Poisson regression model, sample sizes of 81 patients per group will provide 80% power to detect a 68% reduction in unplanned missed days and a 72% reduction in unplanned hospital admissions in the intervention group compared to the control group (2-sided test, significance level 0.05).

Aim 3

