Analysis. We will assess costs associated with healthcare utilization in both intervention and control groups. Medicare reimbursement rates will be used to estimate costs regardless of the age or insurance of the participant. Using the DRG, diagnosis and procedure codes we will determine what Medicare “would have paid” for those services, and will use that as a proxy for cost. Cost of IV fluids will be estimated using wholesale acquisition cost. We will compute a healthcare utilization cost for each participant. Mean differences between the two groups will be analyzed using a two sample *t*-test for independent means. If necessary, data will be transformed to satisfy normality. In addition, we will describe costs associated with the intervention. Data regarding nurse time for preparation of the simulation and delivery of the intervention (in-person and phone contacts) will be collected prospectively during the study period. An hourly cost will be estimated according to hourly rates according to the Wage and Compensation Survey of the Bureau of Labor Statistics. Equipment costs will be measured. We will also determine costs related to the participants. CGs will be surveyed at each intervention contact (during radiation weeks 1 and 3, and at the end of radiation treatment) regarding: (1) any travel expenses for meetings with the intervention nurse and (2) time lost from work and activities due to the intervention, valued at 100% and 60% of the average hourly rate.

Power. A sample size of 81 in each group will provide 90% power of detecting a medium effect size (Cohen's $d=0.5$) difference between the two means. A two-tailed Type I error rate of 0.05 will be assumed.

In summary:

(1) For the power calculation, we focused on our primary hypothesis and outcome in Aim 1 to determine the sample size for our study ($n=162$); for the rest of other 4 Aims, we assessed the powers based on the sample size obtained in Aim 1. We showed that the proposed sample size will provide clinical meaningful effect size with enough statistical power for all the aims we planned to investigate;

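### Aim 5 asks about mean cost, but the plan's transformation and nonparametric rules could replace the mean comparison with a test of something else

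*Combined protocol and SAP*

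**What the plan says.** Section 2.0 opens Aim 5 with the words "Compare the costs of healthcare utilization (unplanned hospital admission, unplanned emergency room visits, and unplanned use of IV fluids" and sets the intervention arm against control.

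Section 6.0, Aim 5 Analysis, builds one total cost per participant. Services are valued at Medicare rates; fluids have their own source: "Cost of IV fluids will be estimated using wholesale acquisition cost". The test is named next: "Mean differences between the two groups will be analyzed using a two sample" *t*-test. The Aim 5 power statement (90% at 81 per arm, d = 0.5, two-sided 0.05) is also about a difference in means. Between the test and the power statement stands the sentence at issue: "If necessary, data will be transformed to satisfy normality".

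The general paragraph of section 6.0 (headed 6.2, 6.7, 6.8), placed before Aim 1, adds two rules: "Variable transformations will be made in cases where distributions are skewed", and "nonparametric procedures will be used where transformations would be inappropriate". It also promises descriptive means.

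Neither place names a transformation, a trigger, a constant to add to zero costs or a way back to the dollar scale. Nothing says that the difference in mean dollars remains the Aim 5 result whatever the distribution looks like.

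**The concern.** A total over admissions, emergency visits and fluids will contain zeros, many small amounts and a few large ones. It will not look normal, so a normality-driven rule would probably be triggered. A t-test on log cost then compares something close to geometric means, and its result depends on the constant added to zeros. A rank test compares orderings. Neither compares mean cost.

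The pricing of fluids adds to this. A cheap item moves a patient off zero, which counts heavily on a log or rank scale and hardly at all in dollars.

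Aim 5 could therefore report a significant cost difference when mean costs are equal or nearly so, or miss a real difference in means. The choice of transformation and constant would be made after the data are seen.

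**Working it through.** **1. The plan's own figure.** Normal approximation with n = 81 per arm and d = 0.5: power = Φ(d√(n/2) − 1.96) = Φ(0.5 × 6.364 − 1.96) = Φ(1.222) = 88.9%. The exact t calculation gives 88.5%. The stated 90% reproduces within rounding and is not in dispute. With 107 per arm (214/2, section 3.0, Projected Enrollment) it is 95%.

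**2. Would the rule be triggered?** The Aim 2 power paragraph says "in the control group we expect means of 0.29 and 0.25 for the number of unplanned missed days and number of unplanned hospital admissions". With Poisson counts, the zero-cost share is exp(−total event rate):
- admissions only: exp(−0.25) = 78%
- plus 0.5 emergency visits per patient: exp(−0.75) = 47%
- plus 1: exp(−1.25) = 29%
- plus 2: exp(−2.25) = 11%

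The emergency-visit rates are assumptions. The 0.25 is pilot-based and Aim 5 follow-up runs to T4, so the zero share may be lower. In every case the distribution is far from normal.

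**3. Simulation inputs.** The documents give no prices and no emergency or fluid rates, so these are assumed: admissions average $12,000 and emergency visits $960, both lognormal with coefficient of variation 1; a fixed price per IV event; Poisson counts; 6,000 trials per scenario.

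**4. No effect at all.** With 0, 0.5, 1 or 2 emergency visits per patient and 81 or 107 per arm, the raw t, Welch, log(cost+1) and Mann-Whitney tests all reject in 4.3-5.7%. The raw t-test does not need a transformation to hold its error rate here. Raw and Welch agree within 0.3 points.

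**5. Equal mean cost, different mix.** Each row keeps the admission mean at $3,000 (0.25 × 12,000 = 0.20 × 15,000 = 0.167 × 18,000 = 0.125 × 24,000). Rejection rates are log(cost+1) / Mann-Whitney / raw t:

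| Intervention arm | 81/arm, admissions only | 81/arm, plus 1 emergency visit | 107/arm, admissions only |
|---|---|---|---|
| 20% fewer admissions at 1.25 times the cost | 9 / 8 / 4% | 6 / 7 / 5% | 10 / 9 / 4% |
| One third fewer at 1.5 times | 17 / 16 / 5% | 7 / 9 / 5% | 21 / 20 / 5% |
| Half as many at twice | 35 / 35 / 6% | 12 / 17 / 6% | 45 / 44 / 5% |

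In the last row at 81 per arm, admissions only, log(cost+1000) rejects in 20% against 35% for log(cost+1). The constant alone moves the answer.

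**6. Only fluid use falls.** IV events drop from 1 to 0.5 per patient at $50 each, admissions stay at 0.25, and there are no emergency visits. Mean cost is 3,000 + 50 = $3,050 against 3,000 + 25 = $3,025, a fall of $25 or 0.8%. The zero-cost share goes from exp(−1.25) = 29% to exp(−0.75) = 47%. Rejection at 81 per arm:
- Welch 4%
- log(cost+1) 34%
- log(cost+1000) 5%
- Mann-Whitney 52%

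For IV prices of $10 to $200, mean cost falls 0.2-3.1%, log(cost+1) rejects in 18-49% and Mann-Whitney in 52%. Across that price range, with 0.5 emergency visits per patient, log(cost+1) gives 9-26%, Mann-Whitney 11-16% and Welch 4-5%. With one visit per patient at $50 (3,000 trials) the figures are about 10-11%, 6% and 4%.

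**7. The opposite failure.** In a simpler model, half of each arm has zero cost, users' costs are lognormal with log-SD 0.8, and the intervention halves the mean among users ($12,000 to $6,000). With 10,000 trials at 81 per arm, the raw t-test has 72% power, Mann-Whitney 28% and log(cost+1) 8%.

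**The case against.** **Low consequence.** Cost is not among the endpoints listed in section 6.1, section 5.2 speaks of describing costs, arm means will be shown anyway, and Aim 2 tests the event counts directly. This stands. It limits the weight of the point, but the p-value attached to Aim 5 could still concern another quantity.

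**The rule is conditional.** The raw t-test is the named analysis, Aim 5's own text mentions transformation only, and the nonparametric route comes from a general paragraph. One could argue that the aim-specific text governs. So the switch is possible, not certain, and the Mann-Whitney figures depend on applying the general rule to Aim 5.

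**The scenarios are chosen.** The plan hypothesises "fewer interrupted treatment courses, unplanned admissions, unplanned emergency room visits, and unplanned use of IV fluids". It does not hypothesise dearer admissions, nor fluids falling alone. Doubling the cost per admission under Medicare pricing needs a large shift in case mix, the mildest mix is nearly harmless, and emergency visits dilute the effect. All of this is fair. The sizes depend on assumptions; the change in what is tested does not.

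**Power.** This is the strongest objection. If admissions and emergency visits both halve at unchanged unit cost, with 0.5, 1 or 2 emergency visits per control patient and 81 per arm, the raw test has 37%, 45% and 61% power. Log(cost+1) or Mann-Whitney has 82%, 93% and 99%. At 107 per arm it is 45%, 54% and 72% against 91%, 97% and 99.7% for the log test. If both fall by 25% (81 per arm), it is 11-18% against 25-45%. The loss is real. Much of the extra power, however, is for event frequency, which Aim 2 already addresses, and a supportive log or rank test can retain it.

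**Conclusion.** The concern holds. The t-test in dollars answers the Aim 5 question and keeps its error rate at these sample sizes. The transformation sentence and the general skewness rule could replace it with a test that is not about mean cost, and the likely shape of the data makes that probable.

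This is not a false-positive problem when the intervention does nothing. It appears when the mix of events changes while mean cost hardly does. The distortion runs from negligible to about 35% rejection at equal means (81 per arm), and to about 50% for a rank test when only cheap fluid use changes and there are no emergency visits. These sizes rest on assumed prices, event rates and independent Poisson counts. The trial's primary conclusion is not affected. The plan should still be changed, because the ambiguity is avoidable and the edit is small.

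**What to change.** - Delete the transformation sentence from Aim 5, and state in the general paragraph that its transformation and nonparametric rules do not apply to the cost comparison.
- Name the Aim 5 result as the difference in arithmetic mean cost per participant, in dollars, with a Welch or bootstrap confidence interval.
- Keep one prespecified log, rank or two-part analysis, with any added constant fixed in advance. Label it supportive and unable to replace the mean difference.

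This takes one deletion, one exemption and one label, with little programming and no new data. The stated power figure for d = 0.5 is unchanged. The cost is the lower power of the dollar-scale test when all event types fall together, which is the reason to retain the supportive analysis.

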Power. Analyses for Aim 4 to examine moderating effects will be primarily exploratory in nature, since it is well-recognized that power for testing interaction effects is not high in trials that are powered to detect main effects, as is the case here.¹¹² When testing interaction of a binary factor occurring with frequency 0.5, power is 0.86 to detect an interactive effect size of 1.0 SDs (e.g., an intervention effect of 1.0 in one subgroup and an effect of 0.0 in the other), using a 2-sided test, significance level 0.05.

Aim 4a: Analyses for Aim 4a will examine if the SDH variables moderate the relationship between the intervention and caregiver outcomes. Effects of potential modifiers of the treatment effect will be examined by including terms for the SDH modifier by treatment interaction effect in the basic ANCOVA model used to test the primary hypothesis. The increase in enrollment from the extension study will provide additional power, as it is well-recognized that power for testing interaction effects is not high in trials that are powered to detect main effects, as was the case with the parent study. When testing interaction of a continuous SDH modifiers and the treatment, power is 0.81 to detect an interactive effect size of 0.40 standard deviations (SD) using a 2-sided test, significance level 0.05, for those measures that will be available in all subjects (e.g. Ohio Opportunity Index). For SDH measures that will only be available in the 96 extension study participants, we will be able to detect an interactive effect size of 0.59 at the same power and significance levels.

Aim 4b: Qualitative interviews will be audio recorded and transcribed, then verified for accuracy by research staff. Any identifiable information will be removed from transcripts, and each will be assigned a

study number. Deidentified data will be analyzed with NVIVO software using thematic analysis. First, the research team, including the PI, will read and reread 5 transcripts to develop a codebook using an inductive approach. Then, all transcripts will be coded by the research team using NVIVO to organize the data. Additional codes, and subsequently categories of codes will be identified. Clusters of categories converged into themes. Each transcript will be read and coded by three members of the research team for interrater reliability.

Aim 5

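### The power summary claims enough power for every aim, but the plan's own Aim 4 text says interaction power is not high and supports it only for a 1.0 SD interaction

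*Combined protocol and SAP*

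**What the plan says.** Section 6.0, under the combined heading 6.2, 6.7, 6.8, ends with a summary. Item (1) says the sample size of 162 was fixed by Aim 1 and, "for the rest of other 4 Aims, we assessed the powers based on the sample size obtained in Aim 1". It concludes that this sample "will provide clinical meaningful effect size with enough statistical power for all the aims we planned to investigate".

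The Aim 4 power paragraph explains why moderation is treated as mainly exploratory: "power for testing interaction effects is not high in trials that are powered to detect main effects", and it adds that this trial is such a case. Its only figure is power 0.86 for an interaction of 1.0 SD with a binary factor present in half the sample, tested "using a 2-sided test, significance level 0.05". The illustration is an effect of 1.0 SD in one subgroup and none in the other.

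The Aim 4a paragraph repeats that interaction power was not high in the parent study and relies on extension enrolment for more. For a continuous modifier it states power 0.81 for 0.40 SD where the measure exists in all subjects, and a detectable 0.59 SD at the same power where it exists only in the 96 extension participants.

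Section 3.0, Projected Enrollment, gives 244 enrolled and 214 analysed after 12% dropout.

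**The concern.** The summary and the Aim 4 paragraph cannot both stand. One says adequate power for meaningful effects was shown for every aim. The other says power for interactions is not high here, and offers a figure only for an interaction that the plan never justifies as clinically meaningful.

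What is at stake is interpretation. The summary is the sentence most likely to be lifted into a report or publication. Someone relying on it could take a non-significant moderation result as evidence that the intervention works equally well across subgroups, which the design could support only for very large differences. Moderation also matters more since the extension, because Aim 4a was added to examine it for social determinants of health.

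**Working it through.** **Inputs.** N = 162, 81 per arm, and the 0.36 SD design effect (Aim 1 power; 0.36 taken as stated); pooled estimate 0.29 SD from the cited meta-analysis (same paragraph); baseline-to-T4 correlation 0.50 (same paragraph); N = 214 (section 3.0); binary factor at frequency 0.5, two-sided 0.05 (Aim 4 power).

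**Formula.** With four equal cells, the interaction contrast in SD units has SE = √(16/N) = 4/√N. With baseline adjustment at correlation 0.50, multiply by √(1 − 0.50²) = 0.866. The detectable interaction at 80% power is (1.960 + 0.842) × SE. Powers in the table use the noncentral t.

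**The plan's figure first.** At N = 162, SE = 4/12.73 = 0.314. For 1.0 SD, 1.0/0.314 = 3.18 and Φ(3.18 − 1.96) = 0.889; the t version gives 0.885. A simulation in which the factor occurs at random gives 0.879. The stated 0.86 is slightly below these and corresponds to N of about 148 to 150. Baseline adjustment gives 0.957. So 0.86 is, if anything, conservative; the difficulty is the size of the interaction it refers to.

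**Size of that interaction.** 1.0/0.36 = 2.8 times the design effect; 1.0/0.29 = 3.4 times the meta-analytic estimate.

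**Smaller interactions.** Aim 4 adds interaction terms to the ANCOVA model used for the primary hypothesis, so the adjusted columns are the relevant ones. Adjusted SE is 0.272 at N = 162 and 0.237 at N = 214.

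| Quantity | N = 162 adjusted | N = 214 adjusted | N = 162 unadjusted | N = 214 unadjusted |
|---|---|---|---|---|
| Power, 0.29 SD | 0.19 | 0.23 | 0.15 | 0.18 |
| Power, 0.36 SD | 0.26 | 0.33 | 0.21 | 0.26 |
| Power, 0.72 SD | 0.75 | 0.86 | 0.62 | 0.75 |
| Detectable at 80% | 0.76 SD | 0.66 SD | 0.88 SD | 0.77 SD |

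The 0.72 SD row is the case where the average effect is 0.36 and one of two equal halves gets no benefit: (0.72 + 0)/2 = 0.36.

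**Aim 4a.** For a continuous modifier per SD, SE = 2/√N. At N = 214, 0.40/0.137 gives power 0.83 against the stated 0.81. With all 96 extension participants counted, 0.59/0.204 gives 0.82. These figures roughly reproduce. They are slopes per SD of the modifier and are not directly comparable with the binary contrast.

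**Sample size cited.** 244 × 0.88 = 214.7, so 214 analysed, or 107 per arm. The summary still says 162, and the Aim 2 and Aim 5 figures are given explicitly for 81 per group. The extension figures appear only in Aim 4a.

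**The case against.** The strongest reply is that nothing is hidden. The Aim 4 paragraph itself gives the exploratory status, the reason and the 1.0 SD size, and power of 0.86 is adequate for the interaction it names. The plan nowhere says that a non-significant interaction will be taken as no moderation. The 0.36 SD yardstick is the reviewer's choice. At the current N with baseline adjustment, the case of no benefit in one half of the sample (0.72 SD) has power 0.86. A larger N also helps the plan, so citing 162 does not inflate any claim.

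Most of this stands, and it limits the point to the summary sentence. It does not remove the contradiction, because the summary claims for all aims what the Aim 4 text denies for one of them.

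Three stronger readings are tempting and are not supported:

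- **Aim 2 also contradicts the summary.** The Aim 2 paragraph openly states "80% power to detect a 68% reduction in unplanned missed days and a 72% reduction in unplanned hospital admissions". Those reductions are large, but they are disclosed, and the documents give no benchmark for a realistic reduction.
- **The trial is powered for Aim 1 only, and Aim 4a is exploratory too.** Aim 3 (81% power for its stated scenario) and Aim 5 (90% at 0.5 SD) have their own figures, which this point does not challenge. The plan labels Aim 4 exploratory, but not Aim 4a.
- **The design cannot detect any realistic moderation.** The 0.72 SD row at N = 214 shows that this is too strong.

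**Conclusion.** The point holds as an internal inconsistency in the power summary, not as an arithmetic error. The textual conflict needs no calculation. Its size depends on the yardstick: for an interaction as large as the 0.36 SD design effect, baseline-adjusted power is about 0.26 at N = 162 and 0.33 at N = 214, and 80% power needs about 0.76 and 0.66 SD.

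These figures assume equal cells, correlation 0.50 and two-sided 0.05. An uneven factor lowers power: at frequency 0.2 and N = 162, unadjusted power even for 1.0 SD is 0.72. Using 0.36 SD is an assumption, since the plan states no minimum important interaction.

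The out-of-date 162 is a secondary defect. It leaves unclear which sample the power statements describe, but it does not itself overstate power. The primary analysis and trial conduct are unaffected.

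**What to change.** Replace the last sentence of summary item (1) with wording to this effect:

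> The sample size was set for Aim 1. Aims 2, 3 and 5 have the detectable effects given in their own paragraphs, calculated for 81 per arm. Aim 4 is exploratory and is not adequately powered for interactions of the size of the Aim 1 design effect. Aim 4a has the detectable interaction sizes stated in its paragraph and no others. Interactions in Aims 4 and 4a will be reported as estimates with confidence intervals, and a non-significant interaction will not be read as absence of moderation.

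State beside it that the current projected analysis sample is 214. If the summary is to cite 214 as the basis for power, the Aim 2, 3 and 5 figures must first be recomputed at about 107 per arm; attaching the existing figures to 214 would create a new mismatch.

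Cost: wording only if the figures stay at 81 per arm, plus a short recalculation if they are updated. Sample size, data collection and the primary analysis do not change. The power claim becomes less favourable.
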